6.6.2. Deaths

The frequency (number and percentage) of patients in the safety analysis set who died and who died within 30 days after last dose of study treatment as well as the reason for death, will be tabulated based on information from the ‘Notice of Death’ and ‘Survival Follow-Up’ eCRFs, by treatment group.

- All deaths;
- Deaths within 30 days after last dose of study treatment;

- Reason for Death:
 - Disease progression;
 - Study treatment toxicity;
 - AE not related to study treatment;
 - Unknown;
 - Other.

In addition, date and cause of death will be provided in individual patient data listing together with selected dosing information (study treatment received, date of first/last administration, dose) and will include the following information:

- AEs with fatal outcome (list preferred terms of AEs with outcome=Fatal, as well as AEs of Grade 5),
- Flag for death within 30 days of last dose of study treatment.

6.6.3. Serious Adverse Events

The frequency (number and percentage) of patients with each of the following will be presented for treatment-emergent SAEs by treatment group:

- SAEs by SOC and PT;
- Related SAEs by SOC and PT.

The listings of all SAEs will also be provided with the relevant information with a flag for SAEs with onset outside of the on-treatment period.

6.6.4. Other Significant Adverse Events

The frequency (number and percentage) of patients with each of the following will be presented for irAEs, by treatment group:

- irAEs leading to death, by Cluster and PT;
- irAEs, by Cluster and PT;
- irAEs, Grade ≥ 3 , by Cluster and PT;
- irAEs leading to discontinuation of avelumab, by Cluster and PT;
- irAEs leading to discontinuation of axitinib, by Cluster and PT;
- irAEs leading to discontinuation of any study drug, by Cluster and PT;

- irAEs leading to discontinuation of all study drugs, by Cluster and PT;
- Serious irAEs, by Cluster and PT.

The listing of all irAEs will also be provided with the relevant information with a flag for irAEs with onset outside of the on-treatment period.

The frequency (number and percentage) of patients with each of the following will be presented for IRRs, by treatment group:

- IRRs leading to death, by PT;
- IRRs, by PT;
- IRRs, Grade ≥ 3 , by PT;
- IRRs leading to discontinuation of avelumab, by PT;
- Serious IRRs, by PT;
- Time related to first onset of an IRR (infusion 1, infusion 2, infusion 3, infusion 4 or later).

The listing of all IRRs will also be provided with the relevant information with a flag for IRRs with onset outside of the on-treatment period.

6.6.5. Laboratory Data

6.6.5.1. Hematology and Chemistry Parameters

Laboratory results will be classified according to the NCI-CTCAE criteria version 4.03. Non-numerical qualifiers (with the exception of fasting flags) will not be taken into consideration in the derivation of CTCAE criteria (eg, hypokalemia Grade 1 and Grade 2 are only distinguished by a non-numerical qualifier and therefore Grade 2 will not be derived). Additional laboratory results that are not part of NCI-CTCAE will be presented according to the categories: below normal limit, within normal limits and above normal limit (according to the laboratory normal ranges).

Quantitative data will be summarized using simple descriptive statistics (mean, SD, median, Q1, Q3, minimum, and maximum) of actual values and changes from baseline for each nominal visit over time (unscheduled measurements would therefore not be included in these summaries as described in [Section 5.2.9](#)). End of Treatment visit laboratory results will be summarized separately. The changes computed will be the differences from baseline. Qualitative data based on reference ranges will be described according to the categories (ie, Low, Normal, High).

Abnormalities classified according to NCI-CTCAE toxicity grading version.4.03 will be described using the worst grade. For those parameters which are graded with two toxicities such as potassium (hypokalemia/hyperkalemia), the toxicities will be summarized separately. Low direction toxicity (eg, hypokalemia) grades at baseline and post baseline will be set to 0 when the variables are derived for summarizing high direction toxicity (eg, hyperkalemia), and vice versa.

For **WBC differential counts** (total neutrophil [including bands], lymphocyte, monocyte, eosinophil, and basophil counts), the absolute value will be used when reported. When only percentages are available (this is mainly important for neutrophils and lymphocytes, because the CTCAE grading is based on the absolute counts), the absolute value is derived as follows:

$$\text{Derived differential absolute count} = (\text{WBC count}) \times (\text{Differential \%value} / 100)$$

If the range for the differential absolute count is not available (only range for value in % is available) then Grade 1 will be attributed to as follows:

- Lymphocyte count decreased:
 - derived absolute count does not meet Grade 2-4 criteria, and
 - % value < % LLN value, and
 - derived absolute count $\geq 800/\text{mm}^3$.
- Neutrophil count decreased:
 - derived absolute count does not meet Grade 2-4 criteria, and
 - % value < % LLN value, and
 - derived absolute count $\geq 1500/\text{mm}^3$.

For **calcium**, CTCAE grading is based on Corrected Calcium and Ionized Calcium (CALCIO). Corrected Calcium is calculated from Albumin and Calcium as follows:

- Corrected calcium (mmol/L) = measured total Calcium (mmol/L) + 0.02 (40 - serum albumin [g/L]).

Liver function tests: Alanine aminotransferase (ALT), aspartate aminotransferase (AST), total bilirubin (TBILI), and Alkaline Phosphatase (ALP) are used to assess possible drug induced liver toxicity. The ratios of test result over upper limit of normal (ULN) will be calculated and classified for these three parameters during the on-treatment period.

Summary of liver function tests will include the following categories. The number and percentage of patients with each of the following during the on-treatment period will be summarized by treatment group:

- ALT $\geq 3 \times \text{ULN}$, ALT $\geq 5 \times \text{ULN}$, ALT $\geq 10 \times \text{ULN}$, ALT $\geq 20 \times \text{ULN}$;

- $AST \geq 3 \times ULN$, $AST \geq 5 \times ULN$, $AST \geq 10 \times ULN$, $AST \geq 20 \times ULN$;
- $(ALT \text{ or } AST) \geq 3 \times ULN$, $(ALT \text{ or } AST) \geq 5 \times ULN$, $(ALT \text{ or } AST) \geq 10 \times ULN$, $(ALT \text{ or } AST) \geq 20 \times ULN$;
- $TBILI \geq 2 \times ULN$;
- Concurrent $ALT \geq 3 \times ULN$ and $TBILI \geq 2 \times ULN$;
- Concurrent $AST \geq 3 \times ULN$ and $TBILI \geq 2 \times ULN$;
- Concurrent $(ALT \text{ or } AST) \geq 3 \times ULN$ and $TBILI \geq 2 \times ULN$;
- Concurrent $(ALT \text{ or } AST) \geq 3 \times ULN$ and $TBILI \geq 2 \times ULN$ and $ALP > 2 \times ULN$;
- Concurrent $(ALT \text{ or } AST) \geq 3 \times ULN$ and $TBILI \geq 2 \times ULN$ and $(ALP \leq 2 \times ULN \text{ or } \text{missing})$.

Concurrent measurements are those occurring on the same date.

Categories will be cumulative, ie, a patient with an elevation of $AST \geq 10 \times ULN$ will also appear in the categories $\geq 5 \times ULN$ and $\geq 3 \times ULN$. Liver function elevation and possible Hy's Law cases will be summarized using frequency counts and percentages.

An evaluation of Drug-Induced Serious Hepatotoxicity (eDISH) plot will also be created, with different symbols for different treatment groups, by graphically displaying.

- peak serum $ALT(/ULN)$ vs peak total bilirubin ($/ULN$) including reference lines at $ALT=3 \times ULN$ and total bilirubin $=2 \times ULN$.
- peak serum $AST(/ULN)$ vs peak total bilirubin ($/ULN$) including reference lines at $AST=3 \times ULN$ and total bilirubin $=2 \times ULN$.

In addition, a listing of all TBILI, ALT, AST and ALP values for patients with a post-baseline $TBILI \geq 2 \times ULN$, $ALT \geq 3 \times ULN$ or $AST \geq 3 \times ULN$ will be provided.

Parameters with NCI-CTC grades available:

The laboratory toxicities will be tabulated using descriptive statistics (number of patients and percentages) during the on-treatment period. The denominator to calculate percentages for each laboratory parameter is the number of patients evaluable for CTCAE grading (ie, those patients for whom a Grade 0, 1, 2, 3 or 4 can be derived).

- The summary of laboratory parameters by CTCAE grade table will include number and percentage of patients with Grade 1, 2, 3, 4, Grade 3/4 and any grade (Grades 1-4), laboratory abnormalities during the on-treatment period.

- The shift table will summarize baseline CTCAE grade versus the worst on-treatment CTCAE grade. The highest CTCAE grade during the on-treatment period is considered as the worst grade for the summary.

The above analyses apply to hematology and chemistry evaluations which can be graded per CTCAE, ie:

- Hematology:

Hemoglobin (HB), Leukocytes (white blood cell decreased), Lymphocytes (lymphocyte count increased/decreased), Neutrophils/Absolute Neutrophils Count (ANC) (neutrophil count decreased), Platelet Count (PLT) (platelet count decreased).

- Serum Chemistry:

Albumin (hypoalbuminemia), Alkaline Phosphatase (alkaline phosphatase increased), Alanine Aminotransferase (ALT) (ALT increased), Amylase (serum amylase increased), Aspartate Aminotransferase (AST) (AST increased), Total Bilirubin (blood bilirubin increased), Cholesterol (cholesterol high), Creatinine (creatinine increased), Creatine Kinase (CPK increased), Potassium (hypokalemia/hyperkalemia), Sodium (hyponatremia/hypernatremia), Magnesium (hypomagnesemia/hpermagnesemia), Calcium (hypocalcemia/hypercalcemia), Glucose (hypoglycemia/hyperglycemia), Gamma Glutamyl Transferase (GGT) (GGT increased), Lipase (lipase increased), Phosphates (hypophosphatemia), Triglycerides (hypertriglyceridemia).

Parameters with NCI-CTC grades not available:

Hematology and chemistry evaluations which cannot be graded per CTCAE criteria will be summarized as frequency (number and percentage) of patients with:

- shifts from baseline normal to at least one result above normal during on-treatment period;
- shifts from baseline normal to at least one result below normal during on-treatment period.

In this study, these apply to the following parameters:

- Hematology: Absolute Monocytes, Absolute Eosinophils, Absolute Basophils;
- Serum Chemistry: Chloride, Total Urea, Uric Acid, Total Protein, C-Reactive Protein, Lactate Dehydrogenase (LDH), troponin (I and T).

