7.1.2. Laboratory Safety Assessments

Hematology, blood chemistry, and urinalysis will be collected at the time points described in the SOA and analysed at local laboratories. They may also be performed when clinically indicated. Clinically significant abnormal laboratory results should be repeated as soon as possible (preferably within 24-48 hours) and followed up as per standard clinical practice unless differently specified in the study protocol.

The required laboratory tests are listed in [Table 5](#)

Table 5. Required Laboratory Tests

Hematology	Chemistry Panel (* denotes core chemistry test)	Urinalysis	Coagulation Tests	Pregnancy Tests
Hemoglobin	ALT*	Protein, glucose, blood	PT or INR	For female patients of childbearing potential, serum or urine
Platelets	AST*		PTT or aPTT	
WBC	Alkaline Phosphatase*	Urine dipstick/other semiquantitative method, for urine protein: if $\geq 2+$, collect 24-hour or UPC		
Absolute Neutrophils or %	Sodium*			
Absolute Lymphocytes or %	Potassium*			
Absolute Monocytes or %	Magnesium*			
Absolute Eosinophils or %	Chloride*			
Absolute Basophils or %	Total Calcium*			
	Total Bilirubin* °			
	BUN or Urea*			
	Creatinine*			
	Glucose (non-fasted)*			
	Phosphorus or Phosphate*			
	Albumin			
	Total Protein			
	Uric Acid			
	Amylase			
	Gamma glutamyl transferase (GGT)			
	Cholesterol			
	Creatine kinase			
	C-reactive protein (CRP)			
	Lactate dehydrogenase (LDH)			
	Lipase			
	Triglycerides			
	HBV, HCV tests**			
	Thyroid Function Tests: TSH, free T4			
	Other Tests: ACTH, α -fetoprotein (AFP), PIVKA-II			

°For potential Hy's Law cases, in addition to repeating AST and ALT, laboratory tests should include albumin, creatine kinase, total bilirubin, direct and indirect bilirubin, gamma glutamyl transferase, prothrombin time (PT or aPT)/INR, alkaline phosphatase.

**HBV, HCV tests: The patients with chronic infection by HBV or HCV will be monitored viral status per standard practice of the study site.

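### Where a laboratory supplies only a percentage normal range, the SAP sets Grade 1 neutrophil and lymphocyte decrease from the percentage, so normal counts can be graded and mildly low counts missed

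*SAP*

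**What the plan says.** SAP 6.6.5.1 uses the reported absolute differential count. If only a percentage is reported, it derives the count as WBC × percentage / 100. The reason it gives is that this matters mainly for neutrophils and lymphocytes, "because the CTCAE grading is based on the absolute counts".

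A fallback follows for laboratories that give no range for the absolute count ("only range for value in % is available) then Grade 1 will be attributed to as follows"). Grade 1 is assigned if three conditions all hold:

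- "derived absolute count does not meet Grade 2-4 criteria, and"
- the percentage is below the laboratory's percentage LLN ("value < % LLN value, and")
- the derived count is at least 800/mm3 for lymphocytes, or at least 1500/mm3 for neutrophils.

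Protocol 7.1.2 has hematology analysed at local laboratories. Its Table 5 accepts either form of result, for example "Absolute Lymphocytes or" percent. Laboratory abnormalities graded by CTCAE v4.03 are part of the primary endpoint (SAP 3.1). They are tabulated by worst on-treatment grade and in shift tables from baseline (SAP 6.6.5.1).

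**The concern.** The fallback grades an absolute toxicity from a relative quantity. Grades 2-4 still come from the derived count, while the boundary between no grade and Grade 1 comes from the percentage, so one scale mixes two measurements. The count condition is a floor without a ceiling: any count above the floor, however high, is Grade 1 once the percentage is low. In the other direction, a count between the floor and an absolute LLN has no route to Grade 1 if the percentage is normal.

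A shift in the differential, such as a rise in neutrophils that lowers the lymphocyte percentage, could then be reported as a decreased lymphocyte count, while mild lymphopenia with a low WBC goes unreported. One draw is enough to set a patient's worst grade. With 20 patients, each misclassified patient moves a percentage by 1/20 = 5 points.

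**Working it through.** **Plan's own figure.** The SAP gives no numerical result for this rule. Its one design figure (at least 88% probability of seeing an AE with 10% incidence in 20 patients) reproduces to rounding as 1 − 0.9^20 = 0.878, and does not bear on this point.

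**Inputs.** From the SAP: derived count = WBC × % / 100, and floors of 800 and 1500/mm3. The documents give no LLN on either scale, so these ranges are assumptions: lymphocytes, % LLN 15-25 and absolute LLN 900-1,500/mm3; neutrophils, % LLN 38-50 and absolute LLN 1,600-2,000/mm3.

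**Single results under the rule as written**

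| Cell | WBC | % | Derived count | Assumed % LLN / absolute LLN | SAP fallback | Against absolute LLN |
|---|---|---|---|---|---|---|
| Neutrophils | 9,000 | 38 | 3,420 | 40 / 1,800 | Grade 1 | not low |
| Lymphocytes | 12,000 | 14 | 1,680 | 20 / 1,000 | Grade 1 | not low |
| Lymphocytes | 3,000 | 28 | 840 | 20 / 1,000 | no grade | Grade 1 |
| Neutrophils | 3,000 | 55 | 1,650 | 40 / 1,800 | no grade | Grade 1 |

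The second and third rows hold across the whole assumed ranges. The first needs a % LLN above 38. The fourth needs an absolute LLN above 1,650.

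**Direction of the error.** At the percentage boundary the two methods agree only when WBC = absolute LLN / (% LLN / 100). For lymphocytes with 1,000 and 20%, that is 1,000 / 0.20 = 5,000. For neutrophils with 1,800 and 40%, it is 1,800 / 0.40 = 4,500. Above that WBC the fallback over-grades, and below it the fallback under-grades. For example, at WBC 3,000 a lymphocyte count from 800 to just under 1,000 corresponds to percentages from 800/3,000 = 26.7% to 1,000/3,000 = 33.3%. All are above a % LLN of 20, so none is graded.

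**Illustrative patient-level size.** This is a simulation of lymphocytes in which every input is assumed: mean WBC 5,500 (CV 25% between and 18% within patients), mean percentage 28 (SD 7 between, 5.5 within), % LLN 20, absolute LLN 1,000, 12 draws, and every laboratory lacking an absolute range. A patient is falsely graded if the rule grades a draw although none is below the absolute LLN. A patient is missed if a draw is below the absolute LLN but the rule grades none.

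- Falsely graded 8.2%; missed 8.8%.
- Any-grade proportion: 60.3% against the absolute LLN, 59.7% under the SAP rule.
- If the absolute LLN is 900, these are 51% and 60%; if it is 1,100, they are 68% and 60%.
- Falsely graded ranges from about 2% to 30% over mean percentage 25-32, % LLN 18-25, absolute LLN 900-1,100 and 6 or 12 draws. It is 26% with mean WBC 8,000.
- For neutrophils (mean 58%, % LLN 40-45, absolute LLN 1,800), 5% to 18% are falsely graded, depending on the assumed spread.

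**Alternative rule.** With a common absolute LLN of 1,000, 9.2% are falsely graded if the laboratory's own LLN is 900, and 8.2% are missed if it is 1,100. The SAP rule's total error (false plus missed) in those two settings is about 17% and 19%.

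**The case against.** **Reach.** The trigger is a missing absolute range, not a result reported as a percentage. A reader might infer from Table 5 and the local laboratories that the fallback will be used. The documents show only that it can be; they do not show that any laboratory lacks an absolute range. Scaling the simulation to 8.2% × 20 = 1.6 and 8.8% × 20 = 1.8 patients assumes that every site is affected, so those figures are not a forecast. This objection stands.

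**Importance.** A reader might also infer that half of the primary endpoint is compromised. The rule touches two toxicities among 5 hematology and 18 chemistry parameters, and only at the edge of Grade 1. Grades 2-4, and so the Grade 3/4 column, still come from the count. There is no hypothesis test or decision rule (SAP 5.1). This stands as well.

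**Offsetting.** In the base case the two errors almost cancel in the any-grade proportion. That is true there, but it depends on the inputs: it fails at absolute LLNs of 900 or 1,100. It also leaves individual patients wrongly classified in the shift table.

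**Other outputs.** Low leukocytes are graded separately, actual values are summarized by visit, and listings flag out-of-range values beside their ranges (SAP 6.6.5.1 and 6.6.5.2). Baseline is graded by the same rule, so a persistently low percentage need not appear as a new shift. These soften the harm, but they do not correct the graded tables or show which grades came from the fallback.

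**The remedy is also a proxy.** The laboratory's own absolute LLN is missing by definition, and a common value will sometimes be wrong. This is correct and is counted as a cost of the change.

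**Conclusion.** The point holds as a defect in a stated rule. The fallback contradicts the SAP's own basis for grading and, followed literally, misgrades in both directions. Over-grading needs little assumption because the count has no ceiling. Under-grading needs only an absolute LLN above the SAP's floor. That such a count is treated as normal is by implication, since the SAP gives it no other grade.

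Confidence is high on the mechanism and low on the size. The number of laboratories without an absolute range is not stated, so the effect in this trial is unknown and could be nil. The simulated percentages depend on assumed blood-count distributions and LLNs. The change should be made because it is cheap and the current rule measures the wrong quantity. It does not put the Grade 2-4 results in doubt.

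**What to change.** In SAP 6.6.5.1, for laboratories with no absolute range, replace the percentage condition for both cell types with: derived absolute count below a prespecified common absolute LLN. Name the value and its source before the database is released, for example the sponsor's standard reference range or the range from study laboratories that report one. Keep the 800 and 1500/mm3 lower bounds and leave Grades 2-4 as they are. Flag grades assigned this way in the laboratory listings, so that the number of affected patients is visible.

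The cost is a short SAP edit, one programming condition and a listing flag, with no new data. The downside is that the common LLN replaces a laboratory-specific limit and will misgrade some patients where the two differ, as quantified in the working above.

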8.4.2. Potential Cases of Drug-Induced Liver Injury

Humans exposed to a drug who show no sign of liver injury (as determined by elevations in transaminases) are termed “tolerators,” while those who show transient liver injury, but adapt are termed “adaptors.” In some patients, transaminase elevations are a harbinger of a more serious potential outcome. These patients fail to adapt and therefore are “susceptible” to progressive and serious liver injury, commonly referred to as drug-induced liver injury (DILI). Patients who experience a transaminase elevation above 3 times the upper limit of normal (\times ULN) should be monitored more frequently to determine if they are an “adaptor” or are “susceptible.”

In the majority of DILI cases, elevations in aspartate aminotransferase (AST) and/or alanine aminotransferase (ALT) precede total bilirubin (TBili) elevations ($>2 \times$ ULN) by several days or weeks. The increase in TBili typically occurs while AST/ALT is/are still elevated above $3 \times$ ULN (ie, AST/ALT and TBili values will be elevated within the same lab sample). In rare instances, by the time TBili elevations are detected, AST/ALT values might have decreased. This occurrence is still regarded as a potential DILI. Therefore, abnormal elevations in either AST OR ALT in addition to TBili that meet the criteria outlined below are considered potential DILI (assessed per Hy’s law criteria) cases and should always be considered important medical events, even before all other possible causes of liver injury have been excluded.

The threshold of laboratory abnormalities for a potential DILI case depends on the patient’s individual baseline values and underlying conditions. Patients who present with the following laboratory abnormalities should be evaluated further as potential DILI (Hy’s law) cases to definitively determine the etiology of the abnormal laboratory values:

- Patients with AST/ALT and TBili baseline values within the normal range who subsequently present with AST OR ALT values $>3 \times$ ULN AND a TBili value $>2 \times$ ULN with no evidence of hemolysis and an alkaline phosphatase value $<2 \times$ ULN or not available;
- For patients with baseline AST **OR** ALT **OR** TBili values above the ULN, the following threshold values are used in the definition mentioned above, as needed, depending on which values are above the ULN at baseline:

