 - Preexisting AST or ALT baseline values above the normal range: AST or ALT values >2 times the baseline values AND $>3 \times$ ULN; or $>8 \times$ ULN (whichever is smaller).

- Preexisting values of TBili above the normal range: TBili level increased from baseline value by an amount of at least $1 \times \text{ULN}$ **or** if the value reaches $>3 \times \text{ULN}$ (whichever is smaller).

Rises in AST/ALT and TBili separated by more than a few weeks should be assessed individually based on clinical judgment; any case where uncertainty remains as to whether it represents a potential Hy's law case should be reviewed with the sponsor.

The patient should return to the investigator site and be evaluated as soon as possible, preferably within 48 hours from awareness of the abnormal results. This evaluation should include laboratory tests, detailed history, and physical assessment.

In addition to repeating measurements of AST and ALT and TBili, laboratory tests should include albumin, CK, direct and indirect bilirubin, GGT, PT/INR, total bile acids, alkaline phosphatase and acetaminophen drug and/or protein adduct levels. Consideration should also be given to drawing a separate tube of clotted blood and an anticoagulated tube of blood for further testing, as needed, for further contemporaneous analyses at the time of the recognized initial abnormalities to determine etiology. A detailed history, including relevant information, such as review of ethanol, acetaminophen (either by itself or as a coformulated product in prescription or over-the-counter medications), recreational drug, supplement (herbal) use and consumption, family history, sexual history, travel history, history of contact with a jaundiced person, surgery, blood transfusion, history of liver or allergic disease, and potential occupational exposure to chemicals, should be collected. Further testing for acute hepatitis A, B, C, D, and E infection and liver imaging (eg, biliary tract) may be warranted.

All cases demonstrated on repeat testing as meeting the laboratory criteria of AST/ALT and TBili elevation defined above should be considered potential DILI (Hy's law) cases if no other reason for the LFT abnormalities has yet been found. **Such potential DILI (Hy's law) cases are to be reported as SAEs, irrespective of availability of all the results of the investigations performed to determine etiology of the LFT abnormalities.**

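### The SAP's same-date rule for possible Hy's Law cases leaves out the rare sequential course that the protocol still treats as potential DILI, so the count can be one case too low

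*SAP*

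**What the plan says.** **SAP 6.6.5.1 (liver function tests).** Five rows combine a transaminase of at least 3×ULN with total bilirubin of at least 2×ULN: ALT, AST, either one, and either one split by ALP. All five are labelled concurrent, and the definition is: "Concurrent measurements are those occurring on the same date". The section adds that possible Hy's "Law cases will be summarized using frequency counts and percentages". No tabulated row uses a time window or peak values.

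The same section plans two displays with no date condition. One is a pair of eDISH plots, setting peak ALT or peak AST against peak bilirubin. The other is a listing of all bilirubin, ALT, AST and ALP values for any patient with a post-baseline elevation of bilirubin (≥2×ULN), ALT (≥3×ULN) or AST (≥3×ULN).

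**Protocol 8.4.2.** Transaminase rises usually come before the bilirubin rise "by several days or weeks", and the bilirubin rise typically comes while AST or ALT is still above 3×ULN, so that both show in one sample. The protocol then adds: "In rare instances, by the time TBili elevations are detected, AST/ALT values might have decreased. This occurrence is still regarded as a potential DILI". On longer gaps it says: "Rises in AST/ALT and TBili separated by more than a few weeks should be assessed individually based on clinical judgment". Cases that meet the laboratory criteria on repeat testing, with no other reason found so far, are reported as SAEs.

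**The concern.** The protocol's category of potential DILI is wider in time than the SAP's count. Rises that do not coincide still belong to the category, and only gaps longer than a few weeks are left to individual judgement. The SAP count has no place for a rise in bilirubin that follows a transaminase peak by days or weeks once the transaminase has dropped below 3×ULN.

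This sits within the primary analysis: laboratory abnormalities are part of the primary endpoint, and SAP 6.1.1.1 refers to section 6.6.5 for their analysis. Protocol 5.4.5.7 names raised liver tests among the toxicities that may overlap between the two drugs, and the patients have hepatocellular carcinoma. A reader of the study report would look to these rows for the number of possible Hy's Law cases, and in a 20-patient safety study none and one read differently.

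**Working it through.** **Design figure.** The plan's only design probability is at least 88% to see one or more AEs in 20 patients at a true incidence of 10% (Protocol 9.1, SAP 5.1.1). It reproduces: 1 − 0.9^20 = 0.878. No figure is stated for Hy's Law cases, so the point turns on the definitions.

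**The two texts side by side.**

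| Course of the liver tests | Protocol 8.4.2 | SAP combined rows |
|---|---|---|
| AST/ALT still raised when bilirubin rises | Typical; potential DILI | Counted |
| AST/ALT has fallen when bilirubin is detected, gap within a few weeks | Rare; still potential DILI | Not counted if AST/ALT is below 3×ULN on the bilirubin date |
| Gap of more than a few weeks | Individual judgement | Not counted |

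The second line is the mismatch. The protocol does not say how far the transaminase must have fallen. It sets the rare course against one in which AST/ALT is still above 3×ULN, so the natural reading includes values below that threshold.

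**A constructed patient** (assumed values, multiples of ULN, normal baseline):

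| Day | ALT | Bilirubin | ALP |
|---|---|---|---|
| 1 | 0.8 | 0.7 | 1.0 |
| 15 | 6.0 | 1.3 | 1.2 |
| 29 | 2.5 | 2.6 | 1.3 |
| 43 | 1.2 | 1.1 | 1.1 |

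- Same-date rule: no day has ALT ≥3 and bilirubin ≥2, so the patient is not counted.
- Bilirubin ≥2 within a window after ALT ≥3: the gap is 29 − 15 = 14 days. A 7-day window misses the patient; windows of 14, 21 and 28 days count the patient.
- Peak against peak: 6.0 and 2.6, so the patient lies beyond both eDISH reference lines (3 and 2).

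**Effect on the reported count, N = 20 (Clopper-Pearson 95% CI).**

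- 0/20: lower limit 0; upper limit 1 − 0.025^(1/20) = 16.8%.
- 1/20 = 5%: lower limit 1 − 0.975^(1/20) = 0.13%; the upper limit solves (1 − p)^20 + 20p(1 − p)^19 = 0.025, giving 24.9%.

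**How likely is it?** The documents give no rate. If q is the true proportion of patients with such a course, the chance of at least one uncounted case is 1 − (1 − q)^20. For assumed q of 1%, 2%, 5% and 10%, this is 18%, 33%, 64% and 88%. The protocol's description of the course as rare points to the lower end.

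**The case against.** The best defence is that the SAP counts the course the protocol calls typical and already displays the rest. The liver listing must include any patient with the sequential course, the eDISH plots show the same patient, and the separate ALT, AST and bilirubin rows count each elevation. A case reported as an SAE in the on-treatment period would also enter the SAE tables (SAP 6.6.3), though by preferred term. With about 20 patients each case can be read individually, and no hypothesis test or decision rule depends on the count. All of this stands, and it limits the point to one tabulated number.

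Four stronger readings are tempting, and the documents do not support them:

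- **Safety information is lost.** It is not; the listing and plots carry it.
- **SAE-reportable cases go missing.** Protocol 8.4.2 makes reporting depend on repeat testing and on no other reason having been found, with thresholds adjusted for raised baselines. The constructed patient shows only the timing gap, not that the case would be reportable.
- **Protocol Table 4 makes the sequential course likely.** Its steroid treatment and testing every 1 to 2 days for higher-grade hepatic events say nothing about the relative timing of ALT and bilirubin. Frequent testing also gives more chances to catch an overlap. Draws on adjacent days are a minor issue, because ALT, AST and total bilirubin are in one chemistry panel (Protocol Table 5).
- **A table and plot that differ are in error.** One is labelled concurrent and the other uses peaks, so they answer different questions.

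What the defence does not answer is that the tabulated count leaves out a course the protocol expressly includes, and the SAP has no step that reconciles the two.

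**Conclusion.** The mismatch is real and narrow. The same-date rule can understate the number of potential DILI cases as the protocol describes them. On timing alone the error runs one way, because a window that includes the same date can never count fewer patients. Its size is at most a case or so in a small table: for one case, 0/20 (0 to 16.8%) in place of 1/20 (0.1 to 24.9%).

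This rests on two readings: that decreased AST/ALT includes values below 3×ULN, and that the gap falls within the protocol's few weeks. How often it would happen cannot be judged from the documents. A reader might infer that the count is generally unreliable. That does not follow, since the typical course is counted correctly.

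**What to change.** Keep the five same-date rows and the definition of concurrent unchanged; stretching that word over several weeks would make the label misleading. Then:

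1. Add one row for patients with bilirubin ≥2×ULN on the same date as, or within a prespecified window after, ALT or AST ≥3×ULN. Give it the same split for ALP ≤2×ULN or missing, with ALP taken on the bilirubin date or the nearest date.
2. Fix one window length in advance. The protocol gives no number; 21 to 28 days is an assumed reading of its wording.
3. In the existing liver listing, flag patients counted only by the window or only by the eDISH quadrant, and reconcile them with potential DILI cases reported as SAEs.

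The cost is a short SAP addition and some programming on data already collected. The downside is specificity. Patients may enter with AST and ALT up to 5×ULN and bilirubin up to 3 mg/dL (Protocol 4.1), and the row uses fixed multiples of ULN. Some rises due to raised baselines or tumour progression will therefore be counted, so the listing should annotate baseline values and alternative causes.
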